8.4 Clinical Laboratory Tests (Coagulation, Serum Chemistry, Hematology, Urinalysis)

Clinical laboratory tests for serum chemistry, hematology, and urinalysis will be performed at Screen, Check-in (Day -1), Hour 8 postdose on Day 1, Day 2, Day 8, Day 29, and Follow-up (Day 36) or prior to early termination. Bleeding time, which is contained in the hematology panel was performed at Check-in (Day -1), Predose, Hour 1 postdose on Day 1, and Day 2. Clinical laboratory tests for coagulation will be performed at Screen, Check-in (Day -1), and Follow-up (Day 36) or prior to early termination, with additional assessments at Hour 1 postdose on Day 1, Day 2, Day 4, Day 8, and Day 29 for PT and INR.

Out-of-normal range flags will be recorded as follows: high (H) and low (L) for numerical results and did-not-match (*) for categorical results. If a value fails the reference range, it will automatically be compared to a computer clinically significant (CS) range. If the value falls within the computer CS range, it will be noted as "N" for not clinically significant. If the value fails (i.e., fall outside of the CS range) the computer CS range, it will be flagged with a "Y" which prompts the PI to determine how the out-of-range value should be followed using 4 Investigator flags: "N", not clinically significant, "R", requesting a recheck, "^", checking at the next scheduled visit, or "Y", clinically significant. To distinguish the PI flag from the computer CS range flags, the PI flags of "N" and "Y" will be presented as "-" and "+", respectively, in the data listing. Additionally, a derived flag based on a search of the PI comments for a comment of "CS" or "Clinically Significant" will be used. The derived flag will be populated with "+" if the positive clinically significant determination is found in the comments for cases when the PI flag is populated with a "^" or a "R".

Out-of-range values and corresponding recheck results will be listed. Results that are indicated as CS by the PI (either in the PI flag or in PI comments) will be listed in a table.

Bleeding time will be listed with the hematology results and will be included in the hematology out-of-range table but will be summarized with the coagulation results.

All coagulation results for PD endpoint aPTT will be listed with the clinical laboratory results and included in the out-of-range table, but for the time points outlined in Section 7.1 summaries will not be included in the clinical laboratory summary tables.

For all numeric laboratory values, descriptive statistics will be presented for each laboratory test by assessment time point and treatment (pooled placebo and xisomab 3G3 dose levels). Change from baseline will be summarized in a similar manner. Baseline is defined as the result closest and prior to dose which may include unscheduled or recheck results. This will typically be the result collected on Day -1.

Postdose unscheduled events or rechecks will not be included in summaries. Similarly early termination results will not be included in summaries.

For each laboratory test, a shift table will be developed to compare the frequency of the results at baseline (above normal, normal, or below normal) with the respective postdose results. For urinalysis tests, the categories are normal and outside normal.

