- c: Subjects for whom aPTT value reaches  $\pm 10\%$  of the baseline value or within the normal range by Day 29, will return to the CRU for the FU visit on Day 36 to perform scheduled follow-up procedures, and to determine if any AE has occurred since the last study visit.  
Subjects for whom aPTT did not reach  $\pm 10\%$  of the baseline value or within the normal range on Day 29, will return every 7 days ( $\pm 2$  days) until aPTT reach  $\pm 10\%$  of the baseline value or within the normal range and for the FU visit (i.e., follow-up procedures and AE evaluation) 7 days ( $\pm 2$  days) after it was reached.  
Subjects who terminate the study early will be asked to continue aPTT monitoring as scheduled until it reaches  $\pm 10\%$  of the baseline value or within the normal range. They will return to the CRU approximately 7 days ( $\pm 2$  days) after aPTT reaches  $\pm 10\%$  of the baseline value or within normal range for the FU visit to perform scheduled follow-up procedures, and to determine if any AE has occurred since the last study visit. They will also be asked to return on Days 15 and 29 to collect the ADA samples.
- d: Subjects will be admitted to the CRU on Day -1, at the time indicated by the CRU.
- e: Symptom-driven physical examination may be performed at other times, at the PI's or designee discretion.
- f: To be performed on Day 29 or at early termination.
- g: To be performed within 24 hours prior to dosing.
- h: Samples for serum chemistry will be obtained following a fast of at least 8 hours (except for the 8-hour time point), however, in case of dropouts or rechecks, subjects may not have fasted for 8 hours before the serum chemistry sample is taken.
- i: If PT/INR values are  $\leq 3.5$  and judged not clinically significant by the PI or designee, the subject will be released from the CRU. Subject will need to return to the CRU at least 2 days after discharge to confirm these values.
- j: Bleeding time will be performed on both subject's arm at each scheduled time point.
- k: To be performed prior to dosing.

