2.2 Endpoints

The primary endpoints of the study will be the number and severity of treatmentemergent adverse events (TEAEs) following single doses of xisomab 3G3 and placebo. Other safety endpoints include clinical laboratories, vital signs, electrocardiograms, physical examinations, and immunogenicity.

- The following PK parameters of free xisomab 3G3 in plasma following single IV dose, will be calculated, as appropriate: AUC0-t, AUC0-inf, AUC%extrap, Cmax, Tmax, Kel, T½, MRT, CL, and Vss.
- aPTT values will be listed with descriptive statistics and presented graphically.

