Programmer note: The following footnote only presented on Coagulation summary tables

Change from baseline summaries for aPTT associated with PD time points can be found Table 14.X.X.X.

Note: Treatment A: < >
Treatment B: < >
Treatment C: < >
Treatment D: < >

Baseline is the last predose measurement.

Program: /CAXXXXX/ECR/sas prg/stsas/tab programname.sas DDMMMYYYY HH:MM

Page 1 of X

Tables 14.3.5.6 (hematology), 14.3.5.9 (urinalysis), and 14.3.5.12 (coagulation & bleeding time) will resemble 14.3.5.3

Page 1 of X Table 14.3.5.3 Clinical Laboratory Shift From Baseline - Serum Chemistry (Safety Population)

			Baseline L		Baseline N		Bas	eline	Н		
		_		Postdo	se	Po	stdos	е		Postdo	ose
Laboratory Test (units)	Treatment	Time Point	L	N	Н	L	N	Н	L	N	Н
Testname (unit)	Х	Day 1 Hour 8	Х	XX	X	X	XX	Х	Х	XX	Х
		Day 2	X	XX	X	X	XX	X	X	XX	X
		Day 8	Χ	XX	X	X	XX	X	X	XX	X
		Day 29	X	XX	X	X	XX	X	X	XX	X
		Follow-up	Χ	XX	X	X	XX	X	X	XX	X
Testname (unit)	X	Day 1 Hour 8	Х	XX	X	Х	XX	X	X	XX	X
		Day 2	Χ	XX	X	X	XX	X	X	XX	X
		Day 8	Χ	XX	X	X	XX	X	X	XX	X
		Day 29	Χ	XX	X	X	XX	X	X	XX	X
		Follow-up	X	XX	X	X	XX	X	X	XX	Χ

Programmer note: Time points are Day 1 Hour 8, Day 2, Day 8, Day 29, and Follow-up. Coagulation time points are Day 1 Hour 1, Day 2, Day 4, Day 8, Day 29, and Follow-up. aPTT samples for PD time points are not presented here. Bleeding time is presented with coagulation with time points Day 1 Hour 1 and Day 2.

Programmer note: For urinalysis, the following footnote is used since the categories of N and O will be used instead of L, N, and H

Note: N = Within reference range, O = Outside reference range

Note: Treatment A: < >
Treatment B: < >

Treatment C: < >

Treatment D: < >

 ${\tt N}$ = Within reference range, L = Below reference range, H = Above reference range Baseline is the last predose measurement.

Change From Baseline Table 14.3.5.14 will resemble 14.3.5.13

Table 14.3.5.13 Vital Sign Summary (Safety Population)

Page 1 of X

	Time Point		Treatment							
Vital Sign (units)		Statistic	А	В	C	D	Pooled Placebo			
Testname (unit)	Screen	n	X	X	X	Х	X			
		Mean	X.X	X.X	X.X	X.X	X.X			
		SD	X.XX	X.XX	X.XX	X.XX	X.XX			
		Minimum	XX	XX	XX	XX	XX			
		Median	X.X	X.X	X.X	X.X	X.X			
		Maximum	XX	XX	XX	XX	XX			
	Baseline	n	X	Х	X	X	X			
		Mean	X.X	X.X	X.X	X.X	X.X			
		SD	X.XX	X.XX	X.XX	X.XX	X.XX			
		Minimum	XX	XX	XX	XX	XX			
		Median	X.X	X.X	X.X	X.X	X.X			
		Maximum	XX	XX	XX	XX	XX			
	Day 1 Hour 0.	25 n	X	X	X	X	X			
	_	Mean	X.X	X.X	X.X	X.X	X.X			

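### Off-schedule lab, vital-sign and ECG results are left out of the planned summaries, and for vital signs and ECGs no other Section 14 table picks them up

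*SAP*

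**What the plan says.** SAP 8.4 sets two exclusions for laboratory summaries: "Postdose unscheduled events or rechecks will not be included in summaries", and "Similarly early termination results will not be included in summaries". Sections 8.5 (vital signs) and 8.6 (ECG) carry the same two sentences. The exclusion is postdose only. Before dosing, off-schedule values can count: "Baseline is defined as the result closest and prior to dose which may include unscheduled or recheck results".

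The shift-table paragraph in SAP 8.4 states no exclusion of its own. Its tables are to "compare the frequency of the results at baseline (above normal, normal, or below normal) with the respective postdose results". The shell in SAP 11.3 settles the matter by its rows: "Time points are Day 1 Hour 8, Day 2, Day 8, Day 29, and Follow-up" for chemistry, with a similar scheduled list for coagulation and bleeding time. It has no unscheduled, early-termination or worst-value row.

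Protocol 12.1.3 says that all laboratory, ECG and vital-sign results, with their changes from baseline, are to be summarized by treatment and collection time point. The flow chart (Protocol Section 6, footnote f) lists several assessments as "To be performed on Day 29 or at early termination". Protocol 12.1 allows the SAP to modify the protocol's analysis plans. SAP Section 9, which exists to list such changes, names only the handling of anti-drug antibodies.

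On the status of these data, SAP 2.2 states "The primary endpoints of the study will be the number and severity of" treatment-emergent adverse events, and then "Other safety endpoints include clinical laboratories, vital signs, electrocardiograms, physical examinations, and immunogenicity".

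**The concern.** Some off-schedule measurements are taken because of a safety question. Protocol 10.3.4 gives serious or clinically significant adverse events and severe laboratory abnormalities among the reasons for stopping early. Protocol 11.1 provides for nonscheduled procedures for urgent safety evaluation, and 11.1.3 to 11.1.5 allow extra vital signs, ECGs and laboratory tests when the investigator thinks them necessary. A summary restricted to planned visits cannot show what those measurements found.

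This is a first-in-human study whose primary objective is safety and tolerability, with four active subjects per dose. A reader who works from the Section 14 tables could see unremarkable vital-sign and ECG rows and not learn that an abnormal value was recorded between visits. The protocol also promises a summary of all results, and nothing in the SAP tells the reader that the promise was narrowed.

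**Working it through.** The documents give no figure on this point to reproduce, so the check is mainly of text and table shells.

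**Where each kind of postdose result is reported** (SAP 8 to 8.6, 10.2, 10.3, 11.3 and 12):

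| Result | By-visit summary and change tables | Shift table | Section 14 abnormal-value table | Listing |
|---|---|---|---|---|
| Lab, scheduled | yes | yes | 14.3.4.1 to .4 if out of range | yes |
| Lab, unscheduled, recheck or early termination | no | no row | 14.3.4.1 to .4 if out of range; 14.3.4.5 for any subject and test with a clinically significant value | yes |
| Vital sign or ECG, scheduled | yes | none planned | none planned | yes |
| Vital sign or ECG, unscheduled, recheck or early termination | no | none planned | none planned | 16.2.8.2, 16.2.8.3 only |

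The last row is the gap. Laboratory abnormalities have a second route into Section 14. Vital signs and ECGs have only Tables 14.3.5.13 to 14.3.5.16, all built on scheduled times.

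**Length of the unscheduled intervals** (SAP 8.4 to 8.6; Day 8 is hour 168 in the flow chart):
- Vital signs and ECG, Hour 0.25 to Day 8: 168 − 0.25 = 167.75 hours.
- Vital signs and ECG, Day 8 to Day 29: 29 − 8 = 21 days.
- Hematology, chemistry and urinalysis, Day 8 to Day 29: also 21 days. An abnormality found and resolved inside that window enters no shift table, though an out-of-range value would be in Tables 14.3.4.1 to 14.3.4.3.

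**Weight of one subject** (SAP Section 5):
- Planned total: 6 + 3 × 5 = 21, of whom 4 × 4 = 16 are active and 2 + 1 + 1 + 1 = 5 are placebo.
- One subject is 1/4 = 25% of a dose group, or 1/5 = 20% of pooled placebo.

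**How often an early termination might arise.** The documents give no rate, so d is an assumption. The chance of at least one among n subjects is 1 − (1 − d)^n:

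| Assumed d | n = 4 (one dose group) | n = 21 (all) |
|---|---|---|
| 5% | 1 − 0.95^4 = 18.5% | 65.9% |
| 10% | 1 − 0.90^4 = 34.4% | 89.1% |
| 20% | 1 − 0.80^4 = 59.0% | 99.1% |

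Over this range at least one early termination somewhere in the study is more likely than not. These figures show that the rule may well be used; they do not show that harm would be hidden.

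**SAP against protocol.** Protocol 12.1.3 covers all results; SAP 8.4 to 8.6 cover scheduled postdose results only; SAP Section 9 is silent. The departure is permitted but unrecorded.

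**The case against.** The case for the plan is substantial, and most of it stands.

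- **Primary analysis.** A reader might infer that the primary safety summaries lose data. They do not. The primary endpoints are adverse events, and the tables of these in SAP 8.3 have no visit-type exclusion. An abnormal finding at any visit can be recorded as an adverse event (Protocol 11.1.9.1), and the shell notes expect clinically significant lab values generally to be captured that way.
- **Nothing is lost.** SAP Section 8 lists all case report form data, including these visits. With 21 subjects the listings can be read in full. Dose escalation rests on the review committee's look at all available data (Protocol 10.4.1.4), not on these tables.
- **Bias toward normal.** A reader might infer that the exclusion must make the drug look safer. The documents do not support a direction. Leaving out a recheck keeps the original scheduled value, so an abnormal first result followed by a normal repeat stays abnormal in the table. Early termination can also follow the subject's own choice, non-compliance or a sponsor decision (Protocol 10.3.4).
- **Day 29.** A reader might infer from footnote f that an early-termination visit is the subject's Day 29 record. The footnote says when procedures are done; it does not assign results to a nominal visit. The SAP's own schedules attach early termination to Follow-up instead. A value drawn at, say, Day 10 would distort a Day 29 mean. A subject who leaves early has no true Day 29 value, and SAP Section 8 handles that openly with reduced denominators. Early terminators are also asked back for a follow-up visit (Protocol 10.1.1), whose results may enter the Follow-up row.
- **Scheduled-only rows are coherent.** The protocol's reference to collection time points can be read as favoring them, and they avoid mixing repeats into a nominal visit.

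These points justify keeping the by-visit rows as they are. They do not supply a Section 14 display for an off-schedule vital sign or ECG, a shift-table row for an off-schedule lab result, or an entry in SAP Section 9.

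**Conclusion.** The concern holds as a gap in reporting and an unrecorded departure from the protocol. Postdose unscheduled, recheck and early-termination results are excluded from the lab, vital-sign and ECG summaries and have no row in the shift tables. For labs the effect is limited, because Tables 14.3.4.1 to 14.3.4.5 carry the abnormal values. For vital signs and ECGs it is complete as far as Section 14 goes: a reading prompted by symptoms between Hour 0.25 and Day 8, between later scheduled visits, or at early termination appears only in a by-subject listing, unless the investigator also records it as an adverse event.

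The scale is one subject in four, or 25% of a dose group, for each affected subject. The number of such subjects, and the direction and size of any bias, cannot be known in advance. The conclusion rests on the shells being programmed as drawn; SAP Section 11 allows them to change. It does not extend to the primary endpoint or to any claim that the plan conceals harm.

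**What to change.** 1. Keep the scheduled-visit rows unchanged, and do not map early-termination results to Day 29.
2. Add a worst-postdose row to shift Tables 14.3.5.3, 14.3.5.6, 14.3.5.9 and 14.3.5.12, drawing on scheduled, unscheduled, recheck and early-termination results. State how a subject with both a low and a high postdose value is counted. The existing rule that keeps the pharmacodynamic aPTT time points out of these tables can stay.
3. Add maximum and minimum postdose change rows to Table 14.3.5.14 (vital signs) and Table 14.3.5.16 (ECG), using the same four sources.
4. Record in SAP Section 9 that by-visit summaries exclude postdose unscheduled, recheck and early-termination results, as a change from Protocol 12.1.3.

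The cost is some table programming on data already collected, with no change to study conduct. The downside is that worst-value rows run more extreme, because abnormal results trigger repeats and each repeat is another chance at an extreme. A footnote should say so and ask that they be read beside the scheduled rows, with pooled placebo shown in the same way.

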8.5 Vital Signs

Vital signs (heart rate, blood pressure, respiration rate, and temperature) will be performed at Screen, predose, Hour .25 postdose on Day 1, as well as Day 8, Day 29, and Follow-up (Day 36) or prior to early termination.

Descriptive statistics will be presented for each vital sign measurement by assessment time point and treatment (pooled placebo and xisomab 3G3 dose levels). Change from baseline will be summarized in a similar manner. Baseline is defined as the result closest and prior to dose which may include unscheduled or recheck results. This will typically be the result collected predose on Day 1. Postdose unscheduled events or rechecks will not be included in summaries. Similarly early termination results will not be included in summaries.

8.6 Electrocardiogram

Single 12-Lead Electrocardiograms will be performed at Screen, predose, Hour .25 postdose on Day 1, as well as Day 8, Day 29, and Follow-up (Day 36) or prior to early termination. ECG parameters include heart rate, PR, QRS, QT, QTcF (QT corrected for heart rate using Fridericia's correction), and overall interpretation.

Descriptive statistics will be presented for each ECG parameter by assessment time point and treatment (pooled placebo and xisomab 3G3 dose levels). Change from baseline will be summarized in a similar manner. Baseline is defined as the result closest and prior to dose which may include unscheduled or recheck results. This will typically be the result collected predose on Day 1. Postdose unscheduled events or rechecks will not be included in summaries. Similarly early termination results will not be included in summaries.

8.7 Concomitant Medications

All concomitant medications recorded during the study will be coded with the WHO Dictionary Version 01MAR2017 and listed.

8.8 Physical Examination

Full physical examinations will be performed at Screen and Check-in (Day -1), and abbreviated physical examinations will be performed at Hour 1 postdose on Day 1, Day 2, Day 29, and Follow-up (Day 36) or prior to early termination. Symptom-

driven physical examinations may be performed at other times, at the PI's or designee's discretion. All data found in the CRF will be listed. Any changes in physical examinations will be captured and summarized with the adverse events and described in the text of the report.

8.9 Medical History

All medical and surgical history will be will be coded using the Medical Dictionary for Regulatory Activities (MedDRA®), Version 20.0 and listed.

8.10 Immunogenicity

Blood samples will be collected from each subject for ADA detection at predose, Day 15, Day 29, and at the Follow-up visit only in the event that the Follow-up visit occurs after Day 36. Immunogenicity testing will be done at Celerion, Lincoln, Nebraska.

A qualitative screening assay will be performed on all samples and results reported as positive or negative for ADA detection. If the screening assay is positive, a qualitative confirmatory assay will be performed on the sample to confirm that the antibodies are specific to xisomab 3G3, with results reported as positive or negative. Confirmed positive samples for ADA will be reassayed, at a series of 2-fold dilutions prior to analysis. The greatest dilution that results in a mean response greater than the assay cut point will be reported as the titer for that sample.

On the other hand, if the screening result is negative, confirmatory and titer assays will not be performed. In the case where the confirmatory result is negative, but the screening result was positive, the titer assay will not be performed.

Results from the qualitative screening and confirmatory ADA detections will be listed as positive or negative. For samples with a positive confirmatory assay, a titer value will be presented with the same level of precision as received from the bioanalytical laboratory.

Frequency counts of positive and negative ADA detection will be presented by collection time, assay type (screening or confirmatory) and treatment (pooled placebo and xisomab 3G3 dose levels).

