#### 8.3.2 Pharmacokinetics

Pharmacokinetics were evaluated in a non-GLP study in baboons (*Papio Anubis*) in which 1 mg/kg of xisomab 3G3 was administered by IV injection and free xisomab 3G3 plasma concentration was measured over time. Non-compartmental analysis of the xisomab 3G3 plasma concentration versus time curve revealed the maximal plasma concentrations normalized to dose ( $C_{\max}/\text{Dose}$ ) was  $19.66 \pm 0.56 \text{ L/kg}$ , the area under the concentration time curve from time 0 to the last time point measured post-dose normalized to dose ( $\text{AUC}_{0-\infty}/\text{Dose}$ ) was  $1594 \pm 82 \text{ kg} \times \text{h/L}$ , and the apparent volume of distribution ( $V_d$ ) was  $0.050 \pm 0.0012 \text{ L/kg}$ . Group mean terminal elimination half-lives ( $T_{1/2}$ ) ranged from 45 to 75 hours and the mean residence time (MRT) ranged from 88 to 110 hours in baboons after a 1 mg/kg IV injection.

In addition, toxicokinetics were evaluated as part of the pivotal toxicity studies in cynomolgus monkey and Sprague Dawley rats. In both studies, IV doses of 0, 2, 10, and 50 mg/kg of xisomab 3G3 were administered by IV bolus injection. All animals except controls showed systemic exposure to xisomab 3G3 following single IV dose. IV infusions of xisomab 3G3 in cynomolgus monkeys resulted in peak free xisomab 3G3 plasma concentrations at the first or second time point evaluated, approximately 0.5 - 3 hours following administration. Maximum concentrations remained generally sustained and therefore the terminal elimination phase was not well characterized for most profiles. In the absence of the recovery data for the main study animals, the terminal elimination phase could only be estimated with confidence for one male who received 10 mg/kg, with  $T_{1/2}$ , CL and  $V_d$  of 31.9 hours, 0.513 mL/h/kg, and 23.6 mL/kg, respectively. Inclusion of the recovery animals ( $n = 2/\text{sex/group}$ ) for all dose levels allowed for better characterization of the terminal elimination phase, however, it could only be estimated for six out of twelve

recovery animals. Consequently, individual  $T_{1/2}$  were longer and ranged from 61.4 to 248 hours. Individual CL and  $V_d$  were estimated between 0.142 and 0.535 mL/h/kg and 34.0 and 57.8 mL/kg, respectively.

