### 11.1.8 Immunogenicity Assessment

Blood samples for immunogenicity assessment will be performed from the PK blood collection tubes as per Study Events Flow Chart ([Section 6](#)).

Instruction for blood sampling, collection, and processing will be provided separately.

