		SD	X.XX	X.XX	X.XX	X.XX	X.XX			
		Minimum	XX	XX	XX	XX	XX			
		Median	X.X	X.X	X.X	X.X	X.X			
		Maximum	XX	XX	XX	XX	XX			

Programmer note: Time points are Screen, Baseline, Day 1 Hour 0.25, Day 8, Day 29, and Follow-up.

Note: Treatment A: < >
 Treatment B: < >
 Treatment C: < >
 Treatment D: < >

Baseline is the last predose measurement.

Change From Baseline Table 14.3.5.16 will resemble 14.3.5.15

Page 1 of X

Table 14.3.5.15 12-Lead Electrocardiogram Summary (Safety Population)

			Treatment							
Measurement (units) Time	Point	Statistic	А	А В		D	Pooled Placebo			
Testname (unit) Scre	en	n	X	Х	X	Х	X			
		Mean	X.X	X.X	X.X	Х.Х	X.X			
		SD	X.XX	X.XX	X.XX	X.XX	X.XX			
		Minimum	XX	XX	XX	XX	XX			
		Median	X.X	X.X	X.X	X.X	X.X			
		Maximum	XX	XX	XX	XX	XX			
Base	line	n	X	Х	X	X	Х			
		Mean	X.X	X.X	X.X	X.X	X.X			
		SD	X.XX	X.XX	X.XX	X.XX	X.XX			
		Minimum	XX	XX	XX	XX	XX			
		Median	X.X	X.X	X.X	X.X	X.X			
		Maximum	XX	XX	XX	XX	XX			
Day	1 Hour 0.25	n	X	X	X	X	X			
		Mean	X.X	X.X	X.X	X.X	X.X			
		SD	X.XX	X.XX	X.XX	X.XX	X.XX			
		Minimum	XX	XX	XX	XX	XX			
		Median	X.X	X . X	X.X	X.X	X.X			
		Maximum	XX	XX	XX	XX	XX			

Programmer note: Time points are Screen, Baseline, Day 1 Hour 0.25, Day 8, Day 29, and Follow-up.

Note: Treatment A: < >
Treatment B: < >
Treatment C: < >
Treatment D: < >

Baseline is the last predose measurement.

Table 14.3.5.17 ADA Detection Summary by Collection Time and Treatment (Safety Population)

				Treatm	Treatment					
Time Point	Assay Type		- - A			D	Pooled Placeb			
Predose	Screening	Negative Positive	X X	X X	X X	X X	X X			
	Confirmatory	Negative Positive	X X	X X	X X	X X	X X			
Day 15	Screening	-	Х	X	X	Х	X			
	Confirmatory	Positive Negative Positive	X X X	X X X	X X X	X X X	X X X			
Day 29	Screening		X	X	X	X	X			
	Confirmatory	Positive Negative Positive	X X X	X X X	X X X	X X X	X X X			
Follow-up	Screening	Negative	X	X	X	X	X			
	Confirmatory	_	X X	X X	X X	X	X X			
Overall*	Screening	Positive Negative	X	X X	X X	X	X X			
	Confirmatory	Positive Negative		X X	X X	X X	X X			
		Positive	X	X	X	X	X			

Note: Follow-up ADA detection sample only collected if Follow-up visit occurred after Day 36.

*For overall counts, if the response of a subject is positive at least once, the subject will be counted as positive; otherwise, the subject will be considered negative.

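### ADA results can only be positive or negative, so a negative screen with free drug above the assay's tolerance counts as negative when it is uninformative

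*SAP*

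**What the plan says.** SAP 8.10 sets the sampling: "Blood samples will be collected from each subject for ADA detection at predose, Day 15, Day 29", plus a follow-up sample only when that visit falls later than Day 36. On results it says: "A qualitative screening assay will be performed on all samples and results reported as positive or negative for ADA detection". Testing stops at a negative screen: "if the screening result is negative, confirmatory and titer assays will not be performed". On the summary: "Frequency counts of positive and negative ADA detection will be presented by collection time, assay type", and also by treatment.

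The shell of Table 14.3.5.17 (SAP 11.3) has only Negative and Positive rows at each time point and overall. The footnote to the overall row reads: "if the response of a subject is positive at least once, the subject will be counted as positive; otherwise, the subject will be considered negative".

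Protocol 11.1.8 says: "Blood samples for immunogenicity assessment will be performed from the PK blood collection tubes". A free-drug concentration from the same draw will therefore normally exist on Days 15 and 29. Protocol 10.1 and 10.2.4 tie the late follow-up sample to aPTT still being prolonged after Day 29, and that visit comes about a week after aPTT recovers.

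Neither document mentions drug tolerance, drug interference, an inconclusive category, or reading an ADA result against the drug level in the same sample.

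**The concern.** The antibodies being sought bind the drug. Enough free drug in the sample can occupy them before the assay does, so a negative screen above the assay's drug tolerance says nothing about whether ADA is present. The plan has nowhere to put such a result except Negative.

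Any error of this kind runs one way, toward negative. Because free drug rises with dose, it would be largest in the highest dose groups. SAP 2.2 lists immunogenicity among the safety endpoints, and Protocol 8.4.1 expects the study to inform Phase 2 dose levels and intervals. A row of 0/4 at the top doses could be read as evidence of low immunogenicity when some or all of those subjects were not assessable.

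**Working it through.** **Plan's own figure.** The documents give no ADA incidence or precision target. The only number to reproduce is the sample size: 6 + 3 × 5 = 21, of whom 4 × 4 = 16 are active and 2 + 3 = 5 placebo. This agrees with Protocol 10.3.1.

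**Inputs.**
- Doses 0.1, 0.5, 2 and 5 mg/kg (Protocol 10.4.1.2). Post-dose ADA at 336 h (Day 15) and 672 h (Day 29).
- Baboon Cmax/Dose 19.66 (Protocol 8.3.2). It is printed in L/kg and read here as kg/L, because 1/19.66 = 0.051 L/kg agrees with the stated Vd of 0.050 L/kg.
- Half-lives (Protocol 8.3.2): baboon 45 to 75 h; rat at 50 mg/kg 155 and 185 h. Monkey values including recovery animals "were longer and ranged from 61.4 to 248 hours".
- Yardstick for measurable drug: PK assay lower limit 50 ng/mL = 0.05 mg/L (SAP 6.2).

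**Residual free drug.** C(t) = dose × 19.66 × 2^(−t/T½), assuming mono-exponential, dose-proportional decline and animal values carried over to humans. Results in mg/L for T½ = 45 / 75 / 155 / 248 h:

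| Dose (mg/kg) | Day 15 | Day 29 |
|---|---|---|
| 0.1 | 0.011 / 0.088 / 0.44 / 0.77 | 0.0001 / 0.004 / 0.097 / 0.30 |
| 0.5 | 0.056 / 0.44 / 2.2 / 3.8 | 0.0003 / 0.020 / 0.49 / 1.5 |
| 2 | 0.22 / 1.8 / 8.7 / 15.4 | 0.001 / 0.079 / 1.9 / 6.0 |
| 5 | 0.56 / 4.4 / 21.9 / 38.4 | 0.003 / 0.20 / 4.9 / 15.0 |

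At any one half-life and time, the 5 mg/kg level is 5/0.1 = 50 times the 0.1 mg/kg level.

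**When drug is measurable.** C(t) reaches 50 ng/mL when T½ ≥ t × ln 2 / ln(C0/50), with C0 in ng/mL. For Day 15 the threshold is 34.9 h at 2 mg/kg and 30.7 h at 5 mg/kg, so both doses clear it over the whole 45 to 248 h range. For Day 29 the thresholds are 126.9, 88.2, 69.9 and 61.4 h from the lowest to the highest dose. Day 29 is therefore open at every dose.

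**Checks on the half-life.** Baboon AUC/Dose over Cmax/Dose is 1594/19.66 = 81.1 h. Times ln 2, that is about 56 h, which at 5 mg/kg gives 1.6 mg/L on Day 15 and 0.025 mg/L on Day 29. Against that, the monkey recovery-animal clearances (0.142 to 0.535 mL/h/kg) are below the baboon value of 1/1594 L/h/kg = 0.627 mL/h/kg and point to longer persistence. One main-study monkey had 31.9 h. At that value Day 15 is 0.066 mg/L at 5 mg/kg and 0.027 mg/L at 2 mg/kg.

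**Evidence that needs no model.** Protocol 8.3.3 reports aPTT prolongation in monkeys to Day 15 at 2 mg/kg and to Day 29 at 10 and 50 mg/kg.

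**Dependence on tolerance.** The documents give none, so 1, 5 and 20 mg/L are assumptions. Doses (mg/kg) whose level exceeds the assumed tolerance:

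| Tolerance (mg/L) | T½ (h) | Day 15 | Day 29 |
|---|---|---|---|
| 1 | 45 | none | none |
| 1 | 75 | 2, 5 | none |
| 1 | 155 | 0.5, 2, 5 | 2, 5 |
| 1 | 248 | 0.5, 2, 5 | 0.5, 2, 5 |
| 5 | 45 or 75 | none | none |
| 5 | 155 | 2, 5 | none |
| 5 | 248 | 2, 5 | 2, 5 |
| 20 | 45 or 75 | none | none |
| 20 | 155 or 248 | 5 | none |

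**Effect on the counts.** The exact two-sided 95% upper limit for 0/n is 1 − 0.025^(1/n): 60.2% for n = 4, 36.9% for n = 8, 20.6% for n = 16. With no positives, a reader who adds the four dose columns gets 0/16. If all 8 subjects at 2 and 5 mg/kg had no conclusive sample, the evidence is 0/8, and those two doses have no evaluable subject.

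**The case against.** The strongest reply is that no bias has been shown. Neither the assay's format nor its tolerance is in the documents, and if the tolerance exceeds the levels present, no count changes. That stands. The missing category is a fact of the text; its effect is conditional.

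Second, subjects with the longest drug effect get a late sample about a week after aPTT recovers, and one positive there makes the subject positive overall. This is a real mitigation. It does not reclassify their Day 15 and Day 29 negatives, and subjects whose aPTT recovers by Day 29 have no later sample.

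Third, individual ADA results (Appendix 16.2.8.4) and concentrations (Tables 14.2.1.1 to 14.2.1.4) are both listed and could be paired by hand. True, but the summary table would still count the sample as negative.

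Fourth, with four active subjects per dose, purely descriptive counts and a 60.2% upper limit for 0/4, nobody should claim absence of immunogenicity or a dose trend. This limits the consequence but does not make the classification right.

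Three stronger readings are tempting and are not supported:
- A reader might infer that every sample drawn with drug on board counts as negative. It does not: one that screens and confirms positive counts as positive.
- A reader might infer that a high half-life, such as the 155 h seen in male rats at 50 mg/kg, is the expected human value. The protocol also reports much shorter ones, at which Day 29 interference is negligible.
- A reader might infer that missing samples are always counted as negative. SAP section 8 uses reduced denominators for missing data, and early terminators are asked back for ADA on Days 15 and 29. The conflict is confined to the overall row, for a subject with no post-dose result.

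**Conclusion.** The concern holds in a conditional form. The two-category rule and the overall footnote count a screen-negative sample as negative whatever its drug level. Measurable free drug on Day 15 at 2 and 5 mg/kg is the firm part: it holds across 45 to 248 h and agrees with the monkey aPTT data. Day 29 ranges from negligible to substantial. Whether the drug present exceeds what the assay tolerates is unknown, so the effect lies between no change and all high-dose negatives being uninformative. At that extreme, 0/16 (20.6%) becomes 0/8 (36.9%). The documents do not support saying that the plan will produce false zeros or a falling dose trend, only that its summary table could not reveal them.

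The concentrations rest on animal values, dose-proportional mono-exponential decline and the kg/L reading of Cmax/Dose.

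**What to change.** In SAP 8.10 and Table 14.3.5.17:
- State the validated drug tolerance of the ADA assay, and pair each ADA result with the free xisomab 3G3 concentration from the same draw.
- Report a screen-negative sample whose concentration exceeds the tolerance as *inconclusive*, in its own row. Positives are unaffected.
- Call a subject negative overall only with at least one conclusive negative post-dose sample, counting the late follow-up sample if taken, and no positive.
- Show the number of evaluable subjects per dose as the denominator.
- Align the overall footnote with the reduced-denominator rule in SAP section 8, so that a subject with no post-dose ADA result is not evaluable rather than negative.

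The cost is SAP wording, one table row and a denominator line. No new visit or blood draw is needed. Where an ADA sample does not coincide with a PK draw, Protocol Table 2 already provides a separate 10 mL tube, and a concentration would have to be run on it. The downside is that fewer subjects can be called ADA-negative at the higher doses. If the tolerance proves to be above every measured level, the new row shows zero and nothing else changes.
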